**A. Title:**

Comparison of the effects of perineural versus systemic dexamethasone on low dose Interscalene Brachial Plexus Block: A randomized trial

**B. Hypothesis**

Perineural dexamethasone added to the local anesthetic ropivacaine for low dose, ultrasound guided interscalene brachial plexus block (US-ISB) provides similar duration analgesia to that of US-ISB with local anesthetic alone and intravenous dexamethasone.

**C. Background and Rationale**

Interscalene brachial plexus block (ISB) is regarded as the standard of care for analgesia after shoulder surgery providing superior analgesia and reducing opioid consumption. ISB can have complications including ipsilateral phrenic nerve block resulting in diaphragmatic paralysis for the duration of the block which can result in temporary ventilatory compromise for patients with reduced respiratory reserve. Nonetheless, the benefits more often outweigh the risks in the appropriate patient population by reducing ventilatory depression associated with significant opioid use after painful upper extremity surgery. Shoulder surgery, previously requiring inpatient admission for pain control, is now commonly performed on an ambulatory basis facilitated by ISB analgesia. The effects of single injection ISB dissipate after several hours unmasking the moderate to severe pain of the surgical insult and require strong opioid analgesia. Efforts to prolong ISB duration by increasing local anesthetic (LA) dose are limited by their pharmacodynamics and narrow therapeutic window.

A broad cross section of surgical patients consistently ranks postoperative pain as their highest concern highlighting the necessity for prolonged and effective postoperative analgesia. Strategies to prolong ISB analgesia include the placement of indwelling perineural catheters to allow for prolonged infusion.

Indwelling catheter techniques can be very effective and provide analgesia for several days but their utility is limited by technical challenges with placement, inherent secondary failure rate, and material cost.

Furthermore, not all anesthesiologists have the subspecialty training required to perform advanced indwelling catheter techniques nor is there universal capability to administer and manage an outpatient perineural catheter program. Centres that do offer outpatient perineural catheter programs are limited by geography in terms of patient eligibility. To address some of these issues, the addition of perineural adjuvants to local anesthetic (eg. clonidine, dexmedetomidine), have been investigated in an attempt to prolong peripheral nerve block duration with limited success. The corticosteroid dexamethasone, has been added to local anesthetic solutions for ISB and has demonstrated promise in preliminary studies. Several studies have demonstrated that perineural dexamethasone in conjunction with local anesthetic prolongs the duration of ISB with effect sizes that range from 40% to 75% (absolute effect ~ 6 to 10 hours) with perineural dexamethasone doses of 8 to 10mg. Postulated mechanisms of action for perineural dexamethasone include attenuating the release of inflammatory mediators, reducing ectopic neuronal discharge, and inhibiting potassium channel mediated discharge of nociceptive C-fibres.

Dexamethasone, however, is only approved for intramuscular or intravenous administration by Health Canada and therefore perineural use is currently off-label. Numerous studies have documented perineural use of dexamethasone without increased incidence of persistent neuropathy. Some concern was expressed with the preservative (sodium bisulfite) in multidose vials causing neurotoxicity. Specific toxicity studies in rat models have documented no histologic changes in nerves when sodium bisulfite (preservative) is directly applied to the nerve at pH7 and a concentration of 0.2% (concentration in commercial preparations of dexamethasone 0.1%). In addition perineural corticosteroid administration

for chronic pain applications (e.g. epidural steroid injection) has a long history of safe administration without evidence of neurotoxicity.

There are several reasons that warrant a new randomized trial. Chiefly, all of the previous trials do not reflect modern regional anesthetic practice. These trials utilized peripheral nerve stimulation (PNS) and local anesthetic volumes of 30 to 40 ml. Modern ultrasound guided ISB (US-ISB) allows for more accurate, targeted deposition of local anesthetic with volumes ranging from 5 to 10 ml with no difference in block efficacy or duration compared to larger volumes ( $\geq 20$ ml). Despite this, critics of low volume US-ISB persist with the belief that low-volume techniques, with their reduced local anesthetic dose, inherently produce a shorter duration block of lesser quality compared to higher volume. However by advocating for higher volume ISB, practitioners guarantee diaphragmatic dysfunction from ipsilateral phrenic nerve block (near 100% with volume  $\geq 10$ ml). An ideal solution would be a local anesthetic with adjuvant mixture that allowed administration of lower volumes but with prolonged analgesic duration. The use of low dose local anesthetic with dexamethasone could be one such solution. A trial that demonstrates enhanced block quality and duration associated with perineural dexamethasone added to low dose local anesthetic may allow us to achieve both prolonged duration of effect and reduced side effects due to unwanted local anesthetic spread. This would create further significant benefits for patients and further promote the use of low dose local anesthetic techniques to anesthesiologists who do not currently use this technique.

Secondly, there is some data to suggest that systemic dexamethasone may also prolong block duration.

The most recent trial failed to show a difference in block duration between systemic and perineural dexamethasone. The conclusions of this trial were that the two modes of administration were equivalent

at prolonging block duration. This was methodologically incorrect, as the trial was not specifically designed as an equivalency trial with defined equivalency margins.

Our trial will add to the literature by determining if systemic dexamethasone is equivalent to perineural dexamethasone in terms of block duration with a properly designed equivalence trial. Should systemic dexamethasone be equivalent to perineural dexamethasone, anesthesiologists will not have to utilize dexamethasone off-label. Should the two administration modalities not be equivalent, anesthesiologists will be able to make informed decisions about its use.

**D. Specific Objective**

To investigate the effect of the addition of perineural dexamethasone (4mg) to ropivacaine on analgesic duration of low dose interscalene block compared to ropivacaine alone for interscalene block with systemic dexamethasone.

**E. Methods**

**i. Inclusion Criteria/Sample population**

1. Patients undergoing arthroscopic shoulder surgery
2. ASA functional status class I to III
3. Age 18 to 80 years
4. BMI  $\leq$  35 kg/m^2

**ii. Exclusion Criteria**

1. Lack of patient consent (including: inability to read or understand the ICF)
2. Allergy to dexamethasone or ropivacaine
3. BMI  $>$  35 kg/m^2

4. Contraindications to low dose dexamethasone including peptic ulcer disease, systemic infection, glaucoma, active varicella/herpetic infections, diabetes mellitus
5. Contraindications to ISB including severe Chronic Obstructive Pulmonary Disease (Forced expiratory volume < 40% predicted), coagulopathy, pre-existing neurologic deficit in ipsilateral upper extremity, localized infection
6. Pregnant or nursing females
7. Chronic opioid use defined as > 30mg oral morphine or equivalent per day
8. Unable to take acetaminophen or celecoxib

iii. **Protocol**

Patients scheduled for arthroscopic shoulder surgery will be approached for participation by research assistants in the pre-operative anesthetic clinic. Patients providing informed consent will be allocated 1:1 in blocks of 10 using a computer generated random number table (randomization will be stratified by site) and blinding of group allocation will be maintained with sequentially numbered, sealed, opaque envelopes.

**The following paragraph outlines standard of care practice (unless otherwise stated) for patients undergoing arthroscopic shoulder surgery at HoAC:**

On the day of surgery, patients will be pre-medicated with oral acetaminophen 1000mg, and oral celecoxib 400mg, unless otherwise stated by the attending physician. Once intravenous access is secure and standard monitors applied (electrocardiogram, non-invasive blood pressure cuff, continuous oxygen saturation), patients will receive sedation with intravenous midazolam (1-2mg). The lateral aspect of the neck including the supraclavicular fossa ipsilateral to the surgical site will be cleansed with standard isopropyl alcohol/chlorhexidine gluconate solution. The US-guided ISB will be performed under sterile conditions by a staff regional anesthesiologist, regional anesthesia fellow, or residents under supervision.

The ISB will be performed using a 13-6 MHz 38-mm linear US probe with appropriate sterile barrier (M-Turbo®; SonoSite Inc., Bothell, WA) at the C6 nerve root level via posterior approach with a 22-gauge insulated 50-mm regional block needle (Stimuplex®; B.Braun Medical, Bethlehem, PA). After satisfactory position of the needle tip is achieved and visualized, the injectate will be administered slowly. The total volume injected is 6 ml to allow for the 1 ml of dead space in the block needle line and needle itself.

Control	Experimental
Ropivacaine 1% 3.5 ml + 0.9% saline 3.5 ml, total volume 7.0ml, final concentration 0.5% ropivacaine Intravenous infusion D5W with dexamethasone 4mg, 50 ml to be infused over 15 minutes	Ropivacaine 1% 3.5 ml + 0.9% saline 2.5 ml, 0.4% dexamethasone 1.0 ml, total volume 7.0 ml, final concentration 0.5% ropivacaine, dexamethasone 4mg Intravenous infusion D5W, 50ml

Dexamethasone has been sourced from Sandoz which contains sodium bisulfite, but not the preservative benzyl alcohol which is present in other preparations. The local anesthetic injectate will be prepared in a blinded syringe by trained block room nurses that are aware of group allocation but will take no further part in study procedures or assessments. This individual will prepare the injectate in a 10ml syringe labelled as followed 'ropivacaine 0.5% +/- dexamethasone 4mg' as well as the intravenous infusion labelled 'saline placebo or dexamethasone 4mg'. All other personnel - patients, anesthesiologists performing the ISB or caring for the patient in the operating theatre, anesthesia assistants, surgeons, research assistants performing outcome measures, and statisticians - will remain blinded.

**The following two paragraphs outline standard of care practice (unless otherwise stated) for patients undergoing arthroscopic shoulder surgery at HoAC:**

Patients will undergo general anesthesia with a standardized induction technique using fentanyl 1 - 4mcg/kg, and propofol 1-3mg /kg both at the discretion of the attending anesthesiologist and titrate to effect. Endotracheal intubation will be facilitated with rocuronium 0.6-1.0mg/kg if necessary or a

laryngeal mask airway can be placed for spontaneously breathing patients. Anesthesia will be maintained using the inhalational anesthetic sevoflurane (AbbVie) with an end-tidal concentration of 1.4 - 2%. The surgeon will infiltrate the arthroscopic port insertion sites with 10-40ml total volume of bupivacaine 0.25% (1:200,000 epinephrine) or lidocaine (as determined by the attending physician). Muscle relaxation will be reversed using a combination of neostigmine (0.04mg/kg) and glycopyrrolate (0.007mg/kg) if necessary. Standard anti-emetic prophylaxis with the serotonin antagonist ondansetron (4mg) will be given. For the purpose of this study, patients will not receive additional dexamethasone regardless of group allocation.

Upon arrival to the recovery room, pain (Verbal Response Score  $\geq 4$  or patient request for analgesia) will be treated with intravenous hydromorphone (solely for this study) in 0.2-0.4mg increments every 5 minutes as needed. Postoperative nausea will be treated (as needed) with an additional dose of ondansetron (1mg), droperidol (0.625mg), dimenhydrinate (50mg) or prochlorperazine at the discretion of the attending physician. Capillary blood glucose will also be assessed and recorded for this study. Once oral intake is initiated, patients will receive one of several analgesic preparations as needed: Tylenol #3® (acetaminophen 325 mg/codeine 30 mg/cafeine 15 mg per tablet), or oxycocet (acetaminophen 325 mg/oxycodone HCl 5 mg per tablet), oxycodone 5-10 mg, or hydromorphone 2-4 mg if intolerant to codeine at the discretion of the attending physician. Upon discharge from hospital, patients will receive a prescription for Tylenol #3® as needed, or hydromorphone or oxycocet if intolerant to codeine at the discretion of the attending physician.

After discharge, patients will complete a home pain diary with information that will be collected by research personnel during postoperative telephone calls. Patients will be asked to record the time at which they first experience pain at the surgical site, the time when they first consumed prescribed opioid

analgesics for surgical site pain and when they regained preoperative baseline hand strength.

Postoperatively patients will be requested to document interval oral analgesic consumption, presence of nausea or vomiting, presence of weakness in the operative arm, and presence of paresthesia (numbness or tingling) in the operative arm. The doses of oral codeine, hydromorphone, or oxycodone consumed by each patient will be converted into equianalgesic doses (oral morphine equivalents). Conversion ratios will be employed according to the general monograph for opioids in the Canadian Pharmacists' Association Compendium of Pharmaceuticals and Specialties (36th ed., 2001) as follows: oral oxycodone: oral morphine sulphate = 1:1.5, oral hydromorphone:oral morphine sulphate = 1:5, and oral codeine: oral morphine sulphate = 6.6:1. The Opioid conversion table has been appended to this protocol.

All patients will be followed-up by telephone on post operative days 1 and 7 (+/- up to 5 days depending on patient availability) to collect the following study data: NRS pain scores, onset of pain and return of the affected hand to normal strength; side effects or complications experienced [(e.g. paresthesia - numbness or tingling, infection at ISB site) in the operative arm, and whether the numbness or tingling was located distal or proximal to the operative site]; and, the quantity, frequency and onset of opioid consumption.

Additional information will not be asked, however if an adverse event (AE) was mentioned during telephone follow-up visits, this will be documented in the AE log and assessed accordingly by the QI.

Additional follow-up telephone visits may be conducted as required in the event of a Serious Adverse Event (SAE) or Adverse Reaction (AR) and will be reported in accordance with the Site Guidance on Safety Reporting document

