**v. Secondary Outcomes**

- Time to first opioid consumption – from end of injection to time to first oral opioid consumption
- Duration of motor block - from end of injection to time of baseline preoperative biceps and hand strength
- Oxygen saturation on room air 1 hour after arrival to recovery room
- Opioid consumption on POD 1 at 12 hours/bed time if patient retires to bed before the 12hr time point), 24 hours and 7 days
- NRS for pain at 12hrs/Bed time (if patient retires to bed before the 12hr time point), 24hours, 7 days
- Blood glucose in recovery room
- Persistent paresthesia in the operative arm at 7 days
- Localized infection at block site at 7 days
- Postoperative nausea

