**vii. Statistical analysis**

Demographic data will be summarized and expressed using appropriate measures of central tendency and dispersion for continuous data, means and standard deviations will be provided (medians and interquartile ranges for non-normally distributed data) and for categorical data counts and percentages will be displayed. The primary outcome, time to first sensation of pain at the surgical site, will be compared between the two groups using a two sample equivalence test of means. Secondary outcomes that are time based will also be assessed in the above manner (time to first analgesic request, duration of motor block). Continuous secondary outcomes (opioid consumption, NRS) will be assessed with repeated measures ANOVA while blood glucose will be assessed with the t-test. Categorical outcomes (paresthesia,

infection, nausea) will be compared with the Chi square or Fisher's exact test for the case of low expected cell counts.

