### Data collection plan

Data will be collected according to the Source-CRFs/CRFs. All data collection will be conducted by a research staff member, either a research assistant or a co-investigator, who is blinded to the patient's treatment allocation.

1. Identifying information, exclusion criteria, surgical procedure description and anesthesia data will be collected preoperatively.
2. Procedure details, including: sedative used, procedure duration (end of injection), pain on injection and the presence of blood will be collected during the block procedure.
3. Pinprick sensation in the C4-T1 dermatomes at 10 and 20 minutes post block (to characterize presence/absence of block). Pain Sensation is characterized as a: (2) = sharp sensation, (1) = dull sensation only, or (0) = no sensation.
4. Motor function (elbow flexion for biceps) at 10 and 20 minutes post block. Power is graded using (2) = normal movement, (1) = reduced movement and (0) = no movement.
5. Intra-operative anesthesia data collection. Time of first Incision, administered anesthesia and time procedure ended.
6. Room air pulse oximetry 1 hour after admission to PACU/recovery room (to characterize respiratory function near discharge)
7. Blood Glucose level in PACU.
8. An account of analgesia administered in PACU.
9. Numerical rating scale (NRS) pain scores 1 hour after admission to PACU to PACU/recovery room
10. Information regarding post block complications (including pain and bruising around the block site) will be collected in a 1 week postoperative telephone call with the patient.
11. Time to first pain sensation in the shoulder, analgesic use and return of the affected hand to normal strength will be captured in the take home patient diary and reported at follow-up telephone calls.
12. NRS pain scores, analgesia consumption and side effects experienced will be captured at: 12hours/bed time, 24 hours and 7 days post-operatively in the patient's diary reported at follow-up telephone calls.

Upon achieving enrolment of the specified 180 patients and data is collected, the database will be verified, and analyzed by the biostatistician.

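### Regular opioid use of up to 30 mg/day is allowed at entry, but the opioid consumption outcome neither separates it nor adjusts for it, which can cost precision on that secondary outcome

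*Combined protocol and SAP*

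**What the plan says.** Section E.ii, item 7, excludes "Chronic opioid use defined as > 30mg oral morphine or equivalent per day". Anyone at or below that dose remains eligible. Randomization is stratified by site only (E.iii).

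For consumption, E.iii states: "Postoperatively patients will be requested to document interval oral analgesic consumption". It continues: "The doses of oral codeine, hydromorphone, or oxycodone consumed by each patient will be converted into equianalgesic doses (oral morphine equivalents". Ratios are given for those three drugs. Neither sentence separates a patient's usual opioid from opioid taken for the operation. E.v lists the outcome as "Opioid consumption on POD 1 at 12 hours/bed time", then at 24 hours and 7 days.

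For first opioid use, the E.iii diary question asks for "the time when they first consumed prescribed opioid" analgesics and limits this to pain at the operated site. The E.v definition of the same outcome, "from end of injection to time to first oral opioid consumption", has no such limit.

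The analysis in E.vii is: "Continuous secondary outcomes (opioid consumption, NRS) will be assessed with repeated measures ANOVA". No preoperative term is named. Item 1 of the data collection plan (E.viii) reads: "Identifying information, exclusion criteria, surgical procedure description and anesthesia data will be collected preoperatively". A preoperative opioid dose is not among the listed items.

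**The concern.** Take two patients with equally good blocks. One continues a usual opioid and needs nothing more; the other took none before surgery. If usual opioid is counted, their totals differ for a reason unrelated to the route of dexamethasone. Every consumption time point is postoperative, so no preoperative value enters the model. Stable usual use therefore stays in the between-patient variation against which the arms are compared.

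Two things are at stake. The comparison becomes less precise, and the arms may by chance contain different numbers of users. In a trial about equivalence, a noisy test that finds no difference in consumption may be taken as support for similarity, an inference that section C itself criticises in an earlier trial. In addition, because the plan does not say whether usual opioid counts, sites or patients may record it differently.

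**Working it through.** **1. The plan's own figure.** The only design figure is for block duration. With SD 4 h, margin 2 h, α = 0.05 per side, true difference 0, and the stated β = 0.9 read as power 0.90:

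n = 2 × [4 × (1.645 + 1.645) / 2]² = 2 × 6.58² ≈ 86.6, so 87 per group.

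This reproduces. It contains no opioid quantity, so the present point does not change it. The plan gives no design figure for opioid consumption.

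**2. The most that usual use can add.** The limit is 30 mg/day (E.ii). Over 24 hours that is 30 mg; over 7 days it is 30 × 7 = 210 mg. By the E.iii ratios, 30 mg oral morphine equivalent is 30 × 6.6 = 198 mg codeine, 30 / 1.5 = 20 mg oxycodone, or 30 / 5 = 6 mg hydromorphone. One Tylenol #3 tablet is 30 / 6.6 = 4.5 mg, so 210 mg is about 46 tablets.

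**3. Illustration of lost precision.** The share of users, their doses and the SD of surgical use are assumptions; none is in the documents. Usual use is taken as independent of surgical use and simply added to it.

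Suppose a share p takes a dose uniform between 5 and 30 mg/day for 7 days. A user's 7-day mean is 17.5 × 7 = 122.5 mg, and the mean square is (17.5² + 25²/12) × 49 = 17,558. The added variance is 17,558p − (122.5p)².

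| p | Mean added (mg) | SD added (mg) | Variance rise, surgical SD 60 mg | Variance rise, surgical SD 100 mg |
|---|---|---|---|---|
| 5% | 6 | 29 | 23% | 8% |
| 10% | 12 | 40 | 45% | 16% |
| 20% | 24 | 54 | 81% | 29% |

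In standard error terms the range is √1.08 to √1.81, an increase of about 4% to 35%.

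**4. Illustration of chance imbalance.** As an upper case, suppose every user takes the full 30 mg/day. The added SD is D√[p(1 − p)], with D = 30 mg at 24 hours and 210 mg at 7 days. The 95% range of the chance difference between arms of 90 is ±1.96 × SD × √(2/90).

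| p | 24 h: SD (mg) | 24 h: imbalance (mg) | 7 days: SD (mg) | 7 days: imbalance (mg) |
|---|---|---|---|---|
| 5% | 6.5 | ±1.9 | 46 | ±13 |
| 10% | 9.0 | ±2.6 | 63 | ±18 |
| 20% | 12.0 | ±3.5 | 84 | ±25 |
| 30% | 13.7 | ±4.0 | 96 | ±28 |

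The expected difference between arms is zero in every row, because allocation is randomized 1:1.

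**The case against.** The strongest reply is that nothing in the documents says usual opioid is counted. The three drugs converted in E.iii are the same ones the trial provides or prescribes after surgery, so the conversion may be meant for those alone. A reader might infer that the outcome is known to measure preoperative use. The documents do not support that: they are silent, and counting is only the natural reading of the unrestricted wording.

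A reader might also take 30 mg and 210 mg as typical. They are worst cases. They need a patient exactly at the limit, a usual drug among the three listed, the full dose continued alongside any new prescription, and a cumulative 7-day total, although E.iii speaks of consumption by interval. If patients replace usual doses with the new prescription, the two do not simply add.

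A third tempting inference is bias. Randomization balances preoperative use in expectation, and chance imbalance is already reflected in the standard error. The unadjusted comparison is valid and its type I error is not inflated.

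Finally, the case report form is not in the documents. E.viii says preoperative details are transcribed from medical records, so the dose may already be captured. Exclusion 7 needs only a yes or no against 30 mg/day, not an exact dose.

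All of this stands, and it limits the severity. What remains is that the plan lists no preoperative dose, uses none in the analysis, and leaves the handling of usual opioid open.

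**Conclusion.** The point holds as a cheap improvement to one secondary outcome. Patients on up to 30 mg/day are eligible, the consumption outcome does not separate usual from surgical opioid, and the planned analysis has no preoperative term. If usual opioid in the three listed drugs is counted, it adds between-patient noise and chance imbalance, bounded by 30 mg at 24 hours and 210 mg over 7 days per patient. The loss could be negligible if few patients are users. Under the assumptions shown, it is an 8% to 81% rise in the variance of the 7-day total. There is no systematic bias between arms. The primary outcome, first sensation of pain, and the 87 per group are unaffected.

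**What to change.** - Record the preoperative daily oral morphine equivalent (0 if none) on the preoperative case report form when exclusion 7 is checked.
- In E.vii, include that dose as a baseline covariate in the analysis of opioid consumption.
- In E.iii and E.v, state whether usual opioid is part of the consumption total.
- Align the E.v definition of first opioid use with the E.iii diary question.
- Optionally, add a sensitivity analysis in patients with no regular preoperative opioid.

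The cost is one form field and one extra model term. Staff already have to ask about daily opioid use to apply exclusion 7, although the exact dose must now be written down. No patients or visits are added, and eligibility and care are unchanged.

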**vi. Sample size calculation**

Based on our clinical experience with low dose US-ISB (ropivacaine 0.5% 5ml) as well as previously published work, we expect mean sensory block duration of 12 hours with a standard deviation of 4 hours.

Based on the literature, we expect a mean prolongation of block time associated with perineural dexamethasone to be approximately 50% thereby increasing block duration to 18 hours. Defining an equivalency margin of 2 hours, we estimate that 87 patients per group (174 total) will be required to reliably test our hypothesis given  $\alpha=0.05$  and  $\beta=0.9$ . To account for incomplete data or loss to follow-up, the plan is to recruit 90 patients per group (180 total).

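### The 4 mg perineural dexamethasone is the amount mixed into 7.0 ml, but only 6 ml is injected, so about 3.43 mg is delivered

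*Combined protocol and SAP*

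**What the plan says.** Section D gives the objective as: "To investigate the effect of the addition of perineural dexamethasone (4mg) to ropivacaine on analgesic duration". The treatment table in section E.iii specifies the experimental syringe as ropivacaine 1% 3.5 ml and saline 2.5 ml, with "0.4% dexamethasone 1.0 ml, total volume 7.0 ml, final concentration 0.5% ropivacaine, dexamethasone 4mg". The text just before the table states: "The total volume injected is 6 ml to allow for the 1 ml of dead space in the block needle line and needle itself". The block room nurse is to "prepare the injectate in a 10ml syringe labelled as followed 'ropivacaine 0.5% +/- dexamethasone 4mg".

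The control arm receives ropivacaine and saline, also 7.0 ml, by the block needle. Its dexamethasone goes by vein: "Intravenous infusion D5W with dexamethasone 4mg, 50 ml to be infused over 15 minutes".

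Section C sets the aim of "determining if systemic dexamethasone is equivalent to perineural dexamethasone in terms of block duration". Section E.vi bases the expected block duration partly on a 5 ml block: "Based on our clinical experience with low dose US-ISB (ropivacaine 0.5% 5ml").

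The documents do not mention a saline chase through the block needle line or extra dexamethasone to cover the dead space. They do not say that 4 mg is a nominal or prepared amount.

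**The concern.** Making up 7.0 ml so that 6 ml can be injected protects the block volume and the ropivacaine concentration, because a concentration does not change when 1 ml is left behind. Dexamethasone is specified differently, as a total mass. Spreading 4 mg over the full 7.0 ml leaves a fixed share of it in volume that is not given.

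Perineural dexamethasone is the experimental intervention, and the trial compares two routes of giving the drug, so the dose by each route is part of the question. The shortfall is systematic: it applies to every perineural patient treated as written, and neither randomisation nor more patients removes it. A report giving the perineural dose as 4 mg, without saying that this is the prepared amount, would misinform anyone who copies the regimen. The use is also off-label and subject to a Health Canada application (section E.ix), which is a further reason to state the dose exactly.

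**Working it through.** **Inputs (treatment table and text of section E.iii)**

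- Dexamethasone 0.4% = 4 mg/ml; volume drawn up 1.0 ml.
- Ropivacaine 1% = 10 mg/ml; volume drawn up 3.5 ml in each arm.
- Saline 2.5 ml (experimental) or 3.5 ml (control).
- Volume injected 6 ml; dead space 1 ml.

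**Step 1: reproduce the plan's figures.**

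- Experimental volume: 3.5 + 2.5 + 1.0 = 7.0 ml. Control volume: 3.5 + 3.5 = 7.0 ml.
- Dexamethasone: 4 mg/ml x 1.0 ml = 4 mg, or 4/7.0 = 0.571 mg/ml.
- Ropivacaine: 10 mg/ml x 3.5 ml = 35 mg, or 35/7.0 = 5 mg/ml = 0.5%.

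The stated 4 mg and 0.5% are both correct for the full 7.0 ml syringe.

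**Step 2: dose delivered = amount in syringe x (volume delivered / 7.0 ml).**

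| Volume leaving the needle tip | Dexamethasone, perineural arm | Shortfall from 4 mg | Ropivacaine, both arms |
|---|---|---|---|
| 7.0 ml (not what the plan describes) | 4.00 mg | none | 35 mg |
| 6 ml | 4 x 6/7 = 3.43 mg | 0.57 mg (14.3%) | 35 x 6/7 = 30 mg |
| 5 ml | 4 x 5/7 = 2.86 mg | 1.14 mg (28.6%) | 35 x 5/7 = 25 mg |

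**Step 3: choose between the readings.** The 6 ml row follows if 1 ml of the 7.0 ml fills the line and needle and the other 6 ml leaves the tip. It accounts for the whole syringe: 7.0 - 1 = 6 ml. The 5 ml row follows if 6 ml is pushed and 1 ml of that stays in the line. It agrees with the 5 ml in section E.vi, but leaves a further 7.0 - 6 = 1 ml in the syringe unexplained. The 6 ml reading is the more natural. Neither gives 4 mg.

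**Step 4: check the sample size.** Two one-sided tests with true difference 0, SD 4 h, margin 2 h, alpha 0.05 and 90% power give n = 2 x (4 x (1.645 + 1.645)/2)^2 = 86.6, rounded up to 87 per group, as stated in section E.vi. The dexamethasone dose does not enter the formula.

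**Step 5: the fill that would deliver 4 mg in 6 ml.** Amount needed in the syringe: 4 x 7/6 = 4.67 mg, which is 4.67/4 = 1.17 ml of 0.4% solution. Saline: 7.0 - 3.5 - 1.17 = 2.33 ml.

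**The case against.** The strongest reply is that each 4 mg statement is true as worded. Section D speaks of adding 4 mg to ropivacaine, the table describes a mixture, and the label describes what is in the syringe. The plan gives both 7.0 ml and 6 ml openly and never says that 4 mg leaves the needle tip. On this view, all that is missing is a clause separating prepared from delivered dose. Much of this stands: a report saying that 4 mg was added to the injectate would be accurate. But section D presents 4 mg as the perineural dose under study, and the procedure as written does not give it.

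A second reply is that no consequence is shown. This is also fair. The documents give no dose-response information between 3.43 mg and 4 mg; the only other perineural doses cited are in section C, "with perineural dexamethasone doses of 8 to 10mg".

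Three stronger readings are tempting and are not supported:

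- A reader might infer that the shortfall biases the comparison of routes or undermines the equivalence conclusion. The documents allow no estimate of any effect on block duration.
- A reader might take 28.6% as the size of the problem. That needs the 5 ml reading, and the 5 ml in section E.vi describes previous experience used to set the expected duration, not the volume delivered in this trial.
- A reader might suppose that the infusion line also holds back drug, so that the intravenous dose is equally uncertain. The table directs that the 50 ml be infused, and the documents give no tubing volume or residual, so there is nothing on which to base that.

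**Conclusion.** The point holds as an error in the stated dose. Followed as written, the plan delivers about 3.43 mg of perineural dexamethasone, 14.3% below the stated 4 mg, against 4 mg assigned intravenously. This assumes a uniformly mixed syringe, 6 ml leaving the needle tip, and no flush or overfill, since none is described. If only 5 ml leaves the tip, the figure is 2.86 mg; the sponsor can settle this.

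Ropivacaine does not differ between the arms on either reading, and the sample size stands. The point should be corrected because the tested dose is a figure the trial relies on and the correction is cheap. It does not show that the trial is invalid or that its result would change.

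**What to change.** First, state in section E.iii the volume that leaves the needle tip. This has to come first, because the dose and any new fill depend on it. Then choose one of two routes.

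**(a) Keep the fill and restate the dose.** In section D, in section E.iii (table and label) and in the trial report, write: 4 mg prepared in 7.0 ml, 3.43 mg delivered in 6 ml, or the figure for the confirmed volume. This costs wording only. It is the route to take if patients have already been treated with the present fill.

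**(b) Change the fill, if 4 mg delivered is intended and the preparation can still be altered.** For 6 ml delivered, use ropivacaine 1% 3.5 ml + saline 2.33 ml + 0.4% dexamethasone 1.17 ml. Amend the label to say that 4 mg is the dose in the delivered 6 ml, because the syringe would then hold 4.67 mg. If 5 ml is confirmed instead, recalculate: 4 x 7/5 = 5.6 mg, or 1.4 ml dexamethasone and 2.1 ml saline.

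Route (b) means less round volumes, more off-label drug in the syringe than is meant to be given, and possible notification of the regulator and ethics boards. Were all 7.0 ml of the 6 ml fill given by mistake, the dose would be 4.67 mg, still below the 8 to 10 mg cited in section C. The volume stays 7.0 ml in both arms, so blinding by volume is unchanged, and neither route needs extra patients.
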